9.4 Statistical Analyses

Statistical analysis will be performed using the computer program package SAS®. More details on the statistical analysis will be presented in the IAP prior to database lock.

The statistical analysis will not be started until all data have been corrected and checked for plausibility, and until all necessary coding and assessments have been completed.

Medical history and AE terms will be coded with the latest version of MedDRA (Version 23.0 or later); concomitant medication will be coded with WHO Drug Dictionary, WHO Drug Reference List and Anatomical Therapeutic Chemical Classification System, latest versions. Versions of dictionaries used for coding will be defined in the Data Management Plan.

All data recorded during the study will be presented in individual data listings.

For demographic (e.g., age, sex, race, etc.), baseline and safety assessments, continuous measurements will be summarized by means of descriptive statistics (i.e., number and percentage of observations, number and percentage of missing observations, mean, SD, median, the Q1 and Q3, Min, and Max) and categorical data will be summarized by means of frequency tables (i.e., count and percentages), if not stated otherwise.

All data will be evaluated as observed, no imputation method for missing values. The handling of concentration values below the limit of quantification will be described in the IAP.

9.4.1 Efficacy Analyses

Not applicable.

9.4.2 Safety Analyses

All safety analyses will be performed on the Safety Analysis Set.

Reference #	Endpoint	Statistical Analysis
Primary		Not applicable
Secondary		
2 - Safety	Nature, occurrence, severity, and seriousness of TEAEs	AE counts and participants with AEs will be summarized for each treatment by SOC and PT. In addition, AEs will be tabulated and listed per participant and analyzed by severity and relationship to study intervention.
	Absolute values and changes in safety laboratory tests from time of first dose to end of study participation	Safety laboratory parameters will be listed for each participant including changes from Baseline and flags for measurements outside the reference ranges, where applicable. Laboratory parameters (hematology and clinical chemistry) will be summarized by time point including both absolute values and changes from Baseline.
	Single 12-lead ECGs evaluated by Investigator from time of first dose to end of study participation	ECG data will be summarized by absolute and changes from Baseline values by treatment using descriptive statistics. Clinical noteworthy ECG findings for individual participants will be listed and summarized as appropriate.
	Vital signs assessed from time of first dose to end of study participation	Vital signs by participant, including changes from Baseline, will be listed and summarized by treatment and time point using descriptive statistics.
CCI		

AE=adverse event; ECG=electrocardiogram; PT=preferred term; SOC=system organ class; TEAE=treatment-emergent adverse event.

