The purpose of this study is to investigate the effect of multiple doses of carbamazepine on single dose evobrutinib PK in healthy participants. Study details include:

[figure not shown]
- Study Duration: up to 54 days.
- Treatment Duration: 25 days.
- Visit Frequency: Participants will be resident in the Clinical Research Unit from Day -1 to Day 20 and return on Day 26 for a Safety Follow-Up visit.

CCI

Study Intervention Groups and Duration: Single-sequence study, 25 days

Involvement of Special Committee(s): No

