1.2 Schema

1.3 Schedule of Activities

Assessments & Procedures	Screening													Safety Follow-Up	Notes	
Study Day	-28 to -2	-1	1	2	3	4	5	6 to 17	18	19	20	21	22	23 to 25	26	
Informed consent	X														Prior to any screening activity.	
Participants resident at CRU		X	X	X	X	X	X		X	X	X	X			X	
Eligibility criteria	X	X														Recheck of eligibility criteria on Day -1, (Sections 5.1 and 5.2).
Demography, height & weight	X															Demography to include, at minimum age (year of birth), sex, race, and ethnicity.
Medical history	X															
Physical examination	X	X													X	Brief examination on Day -1 Section 8.2.1.
FSH	X															In postmenopausal women.
Viral serology, TSH, QuantiFERON® test	X															
Clinical laboratory tests (blood and urine)	X	X						X ^a	X						X	a Safety lab to be collected from Day 10 to Day 14. Appendix 5 and Section 8.2.4.
Cotinine, drug screen, alcohol breath test, SARS-CoV-2	X	X														Appendix 5.
Safety ECG & vital signs	X	X	X	X					X	X	X				X	Predose, 4 and 6 hours postdose on Days 1 and 19. Sections 8.2.2 and 8.2.3.
AE/concomitant medication review	X	X	X	X	X	X	X	X	X	X	X	X	X	X		Section 6.8.
CCI																

Assessments & Procedures	Screening														Safety Follow-Up	Notes
Study Day	-28 to -2	-1	1	2	3	4	5	6 to 17	18	19	20	21	22	23 to 25	26	
Carbamazepine administration, mg				2x 100	2x 100	2x 200	2x 200	2x 300	2x 300	2x 300	2x 200 ^b	2x 200 ^b	2x 200 ^b	2x 100 ^b		First dosing on Day 2 after 24-hour PK sampling for evobrutinib. ^b On Day 20 evening dose, as well as on Days 21 to 25, participants will take carbamazepine at home. Twice daily administration (2x). Section 5.3.1, Section 6.1.
CCI									C C I	C C I					C C I	
Evobrutinib administration			X							X						Section 5.3.1, Section 6.1.
Evobrutinib and metabolite PK blood sampling			X	X						X	X					Sampling Days 1/2 and 19/20: Predose and 0.25, 0.5, 1, 1.5, 2, 2.5, 3, 4, 6, 8, 12, 16 and 24 hours postdose. Section 8.4.

CRU=clinical research unit; ECG=electrocardiogram; FSH=follicle stimulating hormone; PK=pharmacokinetics; SARS-CoV-2=severe acute respiratory syndrome coronavirus 2; TSH=thyroid stimulating hormone.

2 Introduction

Evobrutinib is an oral, selective, irreversible inhibitor of BTK which is in clinical development for the treatment of autoimmune diseases, including RMS.

Detailed information on the chemistry, pharmacology, efficacy, and safety of evobrutinib is in the IB.

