5.3 Lifestyle Considerations

5.3.1 Meals and Dietary Restrictions

Abstain from consumption of the following from 14 days before the start of study intervention until after the final dose: Seville oranges, grapefruit or grapefruit juice, pomelos, exotic citrus fruits, grapefruit hybrids, and their juices.

On Day 1 and Day 19, participants will receive a single dose of 45 mg evobrutinib (tablets) after overnight fasting for at least 10 hours in the morning 0.5 hours after the start of a standard moderate-fat/moderate-calorie breakfast at the CRU. The breakfast should be consumed within 25 to 30 minutes. The start date and time and stop time of the breakfast will be recorded in the participant's eCRFs as well as whether the entire breakfast was consumed. If the entire meal is not consumed, the percentage of meal consumed (in quartiles) should be recorded.

Standard moderate-fat, moderate-calorie breakfasts on evobrutinib dosing days are defined as follows: 490 calories composed of approximately 77 g of carbohydrates, 28 g of protein, and 13 g of fat (Naderer 2015).

All other meals during the inpatient stay at the study center will be standardized and no documentation of time and complete consumption is needed.

On Days 2 to 19, each participant will receive 100, 200 or 300 mg carbamazepine (tablets) twice daily (at least 10 hours apart) during, after, or between meals at the CRU at approximately the same time each day. On Day 19, in the morning, carbamazepine will be co-administered with evobrutinib. The morning carbamazepine dose on Day 20 will be administered at the CRU prior to participants' release from the CRU. Once in the evening of Day 20 and twice daily on Days 21 to 25, participants will take carbamazepine at home.

Study interventions will be administered with 240 mL of water in a standing position at the CRU. On all dosing days (Schedule of Assessments in Section 1.3), participants may consume water ad libitum and should drink at least 1.5 L/day.

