6.1 Study Intervention(s) Administration

Intervention Name	Evobrutinib	Carbamazepine
Type	Drug	Drug
Dose Formulation	Film-coated tablet (TF2)	Tablet with break-line
Unit Dose Strength(s)	45 mg	200 mg (0.5, 1.0 and 1.5 tablet[s])
Dose Amount	45 mg, fed	100 mg (Days 2 and 3), 200 mg (Days 4 and 5), 300 mg (Days 6 to 19), 200 mg (Days 20 to 22) and 100 mg (Days 23 to 25) per administration, fed
Frequency	Single dose on Day 1 and Day 19	Twice daily at the same time each day in the morning and evening (at least 10 hours apart, \pm 1 hour) from Days 2 to 25

Route of Administration	Oral	Oral
Use	Experimental	Experimental
Investigational Medicinal Product	Evobrutinib	Carbamazepine
Supplier	Merck Healthcare KGaA	Merck Healthcare KGaA
Packaging and Labeling	Study intervention will be provided in containers. Each container will be labeled per country requirement. Additional details of packaging and labeling of study intervention will be defined in a separate IMP Handling Manual.	Study intervention will be provided in containers. Each container will be labeled per country requirement. Additional details of packaging and labeling of study intervention will be defined in a separate IMP Handling Manual.

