8.2 Subgroup Definition and Parameterization

Not applicable.

9 General Specifications for Data Analyses

The results of this study will be reported using summary tables, figures, and data listings, as appropriate. All data will be summarized by study intervention and/or scheduled time point, as applicable.

Listings

In the individual participant data listing all individual data will be listed as measured. Repeated and unscheduled measurements will be included in the listings. All listings will be sorted by subject ID and nominal time point, if not stated otherwise.

Tables and Descriptive Statistics

All safety data will be summarized overall by nominal time point, as appropriate. All PK data will be summarized by study intervention and nominal time point. Repeated and unscheduled measurements included in the listings will not be used for statistical analyses or summaries, unless the repeated measurement was performed due to unreliable values/technical reasons, e.g., clotted samples.

Unless otherwise specified, continuous variables will be summarized using descriptive statistics, i.e. the number of participants with non-missing values (n), the number of participants with missing values (nmiss), mean, standard deviation, median, 25th percentile (Q1) and 75th percentile (Q3), minimum, and maximum. If there are no missing values the number of participants with missing values should be indicated by a 0. Mean, Median, Q1, Q3, Min, Max will have the same precision as the SDTM data (decimal places). SD will be presented with one decimal place more than the mean.

Qualitative variables will be summarized by frequency counts and percentages. Unless otherwise stated the calculation of proportions will be based on the number of participants of the analysis set of interest that received the respective study intervention for AE and PK tables and for all other evaluations the analysis set of interest [N]. Therefore, counts of missing observations will be included in the denominator and presented as a separate category.

Study day 1 for this study is defined as the start date of study intervention.

The following labels will be used for the study interventions in PK tables and listings, if not stated otherwise:

Evobrutinib: 45 mg Evobrutinib on Day 1

Carbamazepine+Evobrutinib: Carbamazepine from Day 2 to Day 25 plus 45 mg Evobrutinib on Day 19

All statistical analyses will be performed using SAS® Software version 9.2 or higher.

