15.1.1 All Adverse Events

TEAEs and participants experiencing TEAEs will be summarized overall with:

- The number and percentage of participants with any TEAE, any related TEAE, any evobrutinib-related TEAE, any carbamazepine-related TEAE, any serious TEAE, any related serious TEAE, any evobrutinib-related serious TEAE, any carbamazepine-related serious TEAE, any severe TEAE, any related severe TEAE, any evobrutinib-related severe TEAE, any carbamazepine-related severe TEAE, any AESI, any TEAE leading to death, any related TEAE leading to death, any evobrutinib-related TEAE leading to death, any carbamazepine-related TEAE leading to death, any TEAE leading to study discontinuation
- The number and percentage of participants with at least one TEAE and the number of events by SOC and PT.
- The number and percentage of participants with TEAEs excluding SAEs and the number of events, with frequency $\geq 5\%$ in any study intervention arm by SOC and PT
- The number and percentage of participants with at least one TEAE and the number of events by severity, SOC, and PT

- The number and percentage of participants with at least one related TEAE, evobrutinib-related TEAE, carbamazepine-related TEAE and the number of events by SOC and PT
- The number and percentage of participants with at least one AESI recorded and the number of events by SOC and PT.

Unless otherwise stated, AEs will be displayed with SOC terms sorted alphabetically and PTs within each SOC term sorted in descending overall frequency.

For determining incidence counts, within each level of TEAE term, if a participant experiences more than one occurrence, the participant will only be counted once for that TEAE.

AEs related to any study intervention are those events with relationship missing, unknown or yes.

In case a participant had events with missing and non-missing severity, the maximum non-missing severity will be displayed.

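### Protocol and SAP disagree on whether adverse events are summarised by treatment or overall, and neither form describes evobrutinib given with carbamazepine on a comparable basis

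*Protocol*

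**What the plan says.** **Protocol.** Section 9.4.2 plans that "AE counts and participants with AEs will be summarized for each treatment by SOC and PT", with further tabulation by severity and relationship and listings per participant. It gives no rule for assigning an AE to a treatment and uses no time at risk.

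**SAP.** Section 9 has safety data summarised overall by time point, and section 15 repeats this. Section 15.1 gives TEAEs in total by SOC and PT. Section 15.1.1 opens by saying that TEAEs are summarised overall, and under that lead-in lists "The number and percentage of participants with at least one TEAE and the number of events by SOC and PT". It adds separate tables for evobrutinib-related and carbamazepine-related TEAEs.

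The SAP still carries by-treatment wording in three places:
- Section 9 bases AE percentages on participants who received the respective intervention.
- Section 15.1.1 sets the 5% threshold by study intervention arm, although the study has a single sequence.
- Section 15.1.2 tabulates TEAEs leading to discontinuation by study intervention.

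SAP section 7, on changes from the protocol, mentions only a possible interim data review.

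**Schedule.** Evobrutinib is given as "Single dose on Day 1 and Day 19" (Protocol 6.1). For carbamazepine, Protocol 1.3 specifies "First dosing on Day 2 after 24-hour PK sampling for evobrutinib". Protocol 5.3.1 adds: "On Day 19, in the morning, carbamazepine will be co-administered with evobrutinib". Participants leave the unit on Day 20 and "return on Day 26 for a Safety Follow-Up visit" (Protocol 1.1).

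**The concern.** The secondary safety objective concerns evobrutinib when given together with carbamazepine. A reader of the report will look for what happened in that period and how it compares with evobrutinib alone.

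The protocol's table would set crude counts for periods of very different length side by side. The columns would differ through observation time even if neither drug caused an event. The SAP's overall table avoids that contrast, but it merges events under the combination with those from the preceding 18 days. The tables by drug-relatedness do not separate the periods either, and they rest on investigator judgement in an open-label study.

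Because the documents disagree and the change is not recorded, a programmer could defend producing either table. If the by-treatment one is produced, nothing in the plan defines its columns or warns against comparing them.

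**Working it through.** **Inputs**
- Day 1: evobrutinib alone (Protocol 6.1).
- Day 2, after the 24-hour sample: first carbamazepine dose (Protocol 1.3).
- Day 19, morning: co-administration (Protocol 5.3.1).
- Day 26: Safety Follow-Up (Protocol 1.1), where AE collection ends (Protocol 8.3).
- N = 18, with every participant planned to pass through every period (Protocol 1.1).
- AE rate: not given. It is assumed constant at 0.01 to 0.05 per participant-day, with a wider range tried below.

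**Step 1: period lengths.** The documents define no AE periods, so these are inferred from the dosing days.
- Evobrutinib alone: 2 − 1 = 1 day.
- Carbamazepine alone: 19 − 2 = 17 days.
- Combination: 26 − 19 = 7 days, most of it the carbamazepine taper.
- Sum: 1 + 17 + 7 = 25 days, which agrees with "Treatment Duration: 25 days" in Protocol 1.1.

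**Step 2: expected event counts with no drug effect.** The count is N × rate × days. N and the rate cancel, so the ratio is 1:17:7 at any constant rate. Carbamazepine alone against the combination is 17/7 = 2.4.

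**Step 3: expected participants with at least one AE.** The share is 1 − exp(−rate × days).

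| Rate per day | Evobrutinib alone (1 d) | Carbamazepine alone (17 d) | Combination (7 d) | Combination ÷ evobrutinib | Combination ÷ carbamazepine |
|---|---|---|---|---|---|
| 0.01 | 1.0% | 15.6% | 6.8% | 6.8 | 0.43 |
| 0.03 | 3.0% | 40.0% | 18.9% | 6.4 | 0.47 |
| 0.05 | 4.9% | 57.3% | 29.5% | 6.1 | 0.52 |

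Ratios are taken before rounding. At 0.03 per day and N = 18, the expected numbers of participants are about 0.5, 7.2 and 3.4.

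**Step 4: sensitivity to the rate.** At 0.2 per day the combination still shows 4.2 times as many participants as evobrutinib alone (13.56 against 3.26 of 18). Over 0.005 to 0.2 per day, carbamazepine alone exceeds the combination by 1.3 to 2.4 times.

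**Step 5: the overall table.** Days before co-administration are 1 + 17 = 18 of 25, or 72%.

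**Step 6: time at risk.** Participant-days at N = 18 are 18 × 1 = 18, 18 × 17 = 306 and 18 × 7 = 126, in total 450. Dividing event counts by these returns equal rates in all three periods when there is no drug effect.

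**The case against.** The strongest reply is that the protocol leaves analysis detail to the SAP, and the SAP summarises TEAEs overall. A table with one column has no contrast to distort. This stands as far as it goes: a reader might infer from Protocol 9.4.2 that the final output will show the combination as worse than evobrutinib alone, but SAP 15.1 does not specify that table. It does not settle the matter, because SAP 7 does not record the change and the by-treatment wording in SAP 9, 15.1.1 and 15.1.2 remains.

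Other parts of the reply also stand:
- **The three periods are inferred.** Other boundaries are possible. SAP 9 does have the label "Carbamazepine+Evobrutinib: Carbamazepine from Day 2 to Day 25 plus 45 mg Evobrutinib on Day 19", from which a reader might infer a split of 1 against 24 days for AEs. The SAP introduces its labels for PK tables and listings, so they do not define AE periods.
- **A constant rate is doubtful** while carbamazepine is titrated up, maintained and tapered. The figures show the effect of period length alone and do not forecast the data.
- **The 24 h comparison is limited.** It expects about 0.5 of 18 participants per column at 0.03 per day. The schedule places no safety laboratory test within 24 h after either evobrutinib dose, so laboratory-based events would normally fall outside it. Day 19 also follows 17 days of carbamazepine in a fixed sequence, so the comparison does not isolate an effect of combining the drugs.
- **Listings help.** With 18 participants, a reader can locate events after each evobrutinib dose.

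**Conclusion.** The point holds as an unrecorded inconsistency that leaves the combination without a usable TEAE summary. On the inferred periods and a constant rate, event counts run 1:17:7. At 0.01 to 0.05 AEs per participant-day, participants with an AE under the combination number about 6.1 to 6.8 times those under evobrutinib alone, and about 0.4 to 0.5 times those under carbamazepine alone.

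Two stronger readings are not supported. A reader might infer that the plan cannot serve its safety objective. That objective states no comparison between treatments, the study is purely descriptive (Protocol 9.1), and the severity, seriousness, AESI and relationship summaries and the listings all contribute to it. A reader might also infer a many-fold distortion between every pair of periods, but carbamazepine alone against the combination differs by at most about 2.4-fold. The larger distortion lies only in comparisons with the one-day evobrutinib period.

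**What to change.** 1. Reconcile Protocol 9.4.2 with SAP 9 and 15.1 (including 15.1.1 and 15.1.2), and record the outcome in SAP 7.
2. Define the periods in the SAP, assigning each TEAE by the last intervention started before onset: evobrutinib alone from the Day 1 dose, carbamazepine alone from the first Day 2 dose, combination from the Day 19 co-administration to the Day 26 visit.
3. Add a table of TEAEs with onset 0 to 24 h after the evobrutinib dose, Day 1 against Day 19. This matches the primary PK contrast in the same participants with the same PK sampling times. Evobrutinib's half-life is about 2 hours (Protocol 2.2), so 24 h covers its plasma exposure. BTK inhibition is irreversible, so later effects are possible and the full-period summaries should stay.
4. In any by-period table, show participant-days (about 18, 306 and 126 if all 18 complete) and events per participant-day beside the crude counts. State that crude percentages are not comparable across periods.
5. Correct the onset-from-dosing definition in SAP 9.3, which names products not used in this study and omits carbamazepine.

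The cost is SAP wording and one small table from onset and dosing times already recorded, with no new data or participants. The 24 h table will be sparse and the rates imprecise, so both supplement the overall tables and listings and should be read descriptively.

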9.4.3 Pharmacokinetic Analyses

Details on the PK analysis will be in the IAP that will be finalized before database lock.

Reference #	Endpoint	Statistical Analysis
Primary		
1 – Evobrutinib PK	AUC _{0-∞} and C _{max}	The effect of co-administration of carbamazepine on evobrutinib exposure will be assessed. A general linear model with a fixed effect for TREATMENT and a random effect for SUBJECT will be applied to the log-transformed PK parameters C _{max} and AUC _{0-∞} based on the PK analysis set. Treatment differences on the log scale of evobrutinib with carbamazepine versus evobrutinib alone (Day 19 versus Day 1) will be estimated for the C _{max} and AUC _{0-∞} together with their 90% CIs. Point estimates and CIs will be back transformed to the original scale for presentation. Summary statistics will be provided for AUC _{0-∞} and C _{max} .
Secondary		
3 – Additional evobrutinib PK parameters	CL/F, Vz/F, AUC _{0-tlast} , t _{max} , t _{1/2}	The same analysis model as described for the primary endpoints will be provided for the secondary endpoint AUC _{0-tlast} of evobrutinib in plasma. Summary statistics will be provided for all PK parameters.

4 – Evobrutinib metabolite (MSC2729909A) PK	AUC _{0-∞} , AUC _{0-t_{last}} , C _{max} , t _{max} t _{lag} and the respective metabolic ratios MR(AUC _{0-∞}) and MR(C _{max})	The same analysis model as described for the primary endpoints will be provided for the secondary endpoints C _{max} , AUC _{0-t_{last}} and AUC _{0-∞} of the evobrutinib metabolite MSC2729909A in plasma. Summary statistics will be provided for all PK parameters.
CCI		
CCI		

AUC=area under the concentration-time curve; C_{max}=maximum observed concentration; C_{min}=minimum observed concentration; CL/F=apparent total body clearance; MR=metabolic ratio; PK=pharmacokinetics; t_½=apparent terminal half-life; t_{lag}=time prior to the first measurable (nonzero) concentration; t_{max}=time to reach the maximum observed concentration; Vz/F=apparent volume of distribution.

